#### Grade 1 and 2 Cutaneous Reaction/Rash

A grade 1 cutaneous reaction/rash is defined as localized rash.

A grade 2 cutaneous reaction/rash is defined as diffuse rash or target lesions.

Subjects experiencing a grade 1 or 2 rash or cutaneous event may continue treatment, or have their study medication interrupted at the investigator's discretion. Safety sampling (to be processed by the central laboratory) at the time of the rash and clinical follow-up for these AEs will be at the discretion of the investigator, however, close clinical follow-up is recommended to monitor for any progression of the AE.

#### Grade 3 and 4 Cutaneous Reaction/Rash

A grade 3 cutaneous reaction/rash is defined as:

- Diffuse rash and vesicles or limited number of bullae or superficial ulceration of mucous membrane limited to 1 site;

For the purpose of this protocol, the sponsor considers qualifying as a grade 3 rash the following:

- Cutaneous reaction/rash with at least 1 of the following:
  - elevations of ALT/AST >2 x baseline but  $\geq$ 5 x ULN;
  - fever  $\geq 38^{\circ}$ C or 100°F;
  - serum sickness-like reaction;
  - eosinophil count >1,000/mm^3.
- The syndromes of Drug Reaction with Eosinophilia and Systemic Symptoms (DRESS) and Acute Generalized Exanthematous Pustulosis (AGEP).

A grade 4 cutaneous reaction/rash is defined as:

- Extensive or generalized bullous lesions;
- Stevens-Johnson syndrome (SJS);
- Ulceration of mucous membrane involving at least 2 distinct mucosal sites;
- TEN.

Subjects experiencing a grade 3 or 4 rash or cutaneous event must have their study medication discontinued. Referral to a dermatologist and biopsy are required for these events preferably within 24 hours after the site becomes aware of the cutaneous event/rash.

Safety testing (to be processed by the central laboratory) of the following parameters is required to determine possible liver or systemic abnormalities: ALT, AST, bilirubin (total, direct and indirect), creatinine and a hematology profile. Close clinical follow-up and appropriate medical intervention should be instituted for these events; daily follow-up is recommended for 5 days from the onset of the event to monitor for progression of the event and weekly afterwards as long

as grade 3 or 4 rash is present. Once grade 3 or 4 rash has resolved to  $\leq$  grade 2 rash, follow-up should be done according to the instructions for grade 1 or 2 rash.

DAIDS Toxicity Grade	Definitions	Investigator Action
Grade 1	Localized rash	Subject may continue study medication
Grade 2	Diffuse rash Target lesions	Subject may continue study medication
Grade 3	
 
Diffuse rash and vesicles or limited number of bullae or superficial ulcerations of mucous membrane limited to 1 site
 
For the purpose of this protocol, the sponsor considers qualifying as a grade 3 rash the following:
 
Cutaneous reaction/rash with at least 1 of the following:
 
Elevations in ALT and/or AST (>2 x baseline but ≥5 x ULN)
 
Fever ≥38°C or 100 F
 
Serum sickness-like reaction
 
Eosinophils >1000/mm^3
 
The syndromes of Drug Reaction with Eosinophilia and Systemic Symptoms (DRESS) and Acute Generalized Exanthematous Pustulosis (AGEP)
 
	Permanently discontinue study medication Referral to a dermatologist and biopsy, preferably within 24 hours after the site becomes aware of the cutaneous event/rash Laboratory assessments need to be performed
Grade 4	Extensive or generalized bullous lesions SJS Ulceration of mucous membrane involving at least 2 distinct mucosal sites TEN	Permanently discontinue study medication Referral to a dermatologist and biopsy, preferably within 24 hours after the site becomes aware of the cutaneous event/rash
		Laboratory assessments need to be performed

 Table 3:
 Summary of Cutaneous Reaction/Rash Follow-up

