# 11.5. Efficacy Analyses

#### **Antiviral Efficacy**

The primary analysis will consist of a noninferiority evaluation of switching to the D/C/F/TAF single-tablet regimen (investigational treatment arm) versus maintaining the current regimen consisting of a bPI combined with FTC/TDF (control arm), with respect to the proportion of virologic rebounders through Week 48 after the start of treatment in this study. The rebounders are defined as

- subjects who show confirmed HIV-1 RNA ≥50 copies/mL up to, and including the upper bound of the Week 48 window (ie, 54 weeks),
- subjects who discontinued prematurely (irrespective of reason) for which the last available (single) HIV-1 RNA ≥50 copies/mL.

It will be concluded that the D/C/F/TAF single-tablet regimen is noninferior to the control regimen if the upper bound of the 2-sided 95% confidence interval (CI) of the difference between treatment arms (D/C/F/TAF arm - control arm) in rebounder rate is less than 4% (ie, a margin of 4% is applied to noninferiority assessment). The 2-sided 95% CI will be constructed using the stratum-adjusted Mantel-Haenszel difference in proportions, where the stratification factor (bPI used at screening) determines the strata.

If noninferiority of the D/C/F/TAF arm to control arm is established, the upper bound of the 95% CI will be compared to 0; if the upper bound of the 95% CI is less than 0, then superiority of D/C/F/TAF over the control arm will be established.

The proportion of subjects having confirmed virologic rebound through 24 and 96 weeks of treatment. Treatment difference (with 95% CI) through 24 and 96 weeks will be derived similary as for the primary efficacy parameter.

The proportion of subjects with HIV-1 RNA <20, <50, <200 copies/mL at Weeks 24, 48, and 96, as defined by the FDA snapshot analysis will be analyzed.

In addition, confirmed virologic response defined as HIV-1 RNA <20, <50, and <200 copies/mL at Weeks 24, 48, and 96 determined by the TLOVR algorithm will be analyzed.

The treatment arms will be compared by 95% CIs constructed using the stratum adjusted Mantel-Haenszel difference in proportions at Weeks 24 and 48, where the stratification factor (bPI at screening) determines the strata.

Time to virologic rebound will be graphically presented by means of Kaplan-Meier curves and the treatment groups will be compared by means of the Cox proportional hazards model including terms for treatments and bPI at screening.

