Visual Changes (assessed from baseline)	Visual changes causing no or minimal interference with usual social & functional activities	Visual changes causing greater than minimal interference with usual social & functional activities	Visual changes causing inability to perform usual social & functional activities	Disabling visual loss in affected eye(s)	

SYSTEMIC				
PARAMETER	GRADE 1 MILD	GRADE 2 MODERATE	GRADE 3 SEVERE	GRADE 4 POTENTIALLY LIFE- THREATENING
Acute Allergic Reaction	Localized urticaria (wheals) with no medical intervention indicated	Localized urticaria with intervention indicated OR Mild angioedema with no intervention indicated	Generalized urticaria OR Angioedema with intervention indicated OR Symptoms of mild bronchospasm	Acute anaphylaxis OR Life-threatening bronchospasm OR Laryngeal edema
Chills	Symptoms causing no or minimal interference with usual social & functional activities	Symptoms causing greater than minimal interference with usual social & functional activities	Symptoms causing inability to perform usual social & functional activities	NA
Cytokine Release Syndrome 	Mild signs and symptoms AND Therapy (ie, antibody infusion) interruption not indicated	Therapy (ie, antibody infusion) interruption indicated AND Responds promptly to symptomatic treatment OR Prophylactic medications indicated for ≤24 hours	Prolonged severe signs and symptoms OR Recurrence of symptoms following initial improvement	Life-threatening consequences (eg, requiring pressor or ventilator support)
Fatigue or Malaise Report only one	Symptoms causing no or minimal interference with usual social & functional activities	Symptoms causing greater than minimal interference with usual social & functional activities	Symptoms causing inability to perform usual social & functional activities	Incapacitating symptoms of fatigue or malaise causing inability to perform basic self-care functions
Fever (non-axillary temperatures only)	38.0 to <38.6°C or 100.4 to <101.5°F	≥38.6 to <39.3°C or ≥101.5 to <102.7°F	≥39.3 to <40.0°C or ≥102.7 to <104.0°F	≥40.0°C or ≥104.0°F

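### The fever criterion that turns a rash into grade 3, and so ends study treatment, gives two cut-offs that are not the same temperature (38 °C and 100 °F)

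*Protocol*

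**What the plan says.** Section 9.5.2 of the protocol adds a sponsor-specific definition of grade 3 rash to the standard grading. The entry condition is "Cutaneous reaction/rash with at least 1 of the following", followed by four items: transaminase elevation, fever, a serum sickness-like reaction, and eosinophilia. The fever item in Table 3 is "Fever ≥38°C or 100 F". The running text of the section gives the same pair of numbers, with a degree sign on the Fahrenheit value.

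The prescribed action depends on the grade:

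- Grade 1 or 2: "Subjects experiencing a grade 1 or 2 rash or cutaneous event may continue treatment", or treatment may be interrupted, at the investigator's discretion.
- Grade 3 or 4: "Subjects experiencing a grade 3 or 4 rash or cutaneous event must have their study medication discontinued". Table 3 is stronger: "Permanently discontinue study medication". Dermatology referral, biopsy and laboratory tests are also required.

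Attachment 2, the DAIDS table that the protocol adopts for grading, defines grade 1 fever as "38.0 to <38.6°C or 100.4 to <101.5°F".

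**The concern.** The criterion is written as one threshold in two units, but the two numbers are different temperatures. Fever alone is enough to move a localized or diffuse rash to grade 3, so the choice of number can by itself decide whether a suppressed subject keeps the regimen or must stop it. If the values are taken as equivalents, a site that measures in Fahrenheit and a site that measures in Celsius apply different rules. The SAP (Section 2.7.1) lists Europe and North America as regions, so use of both units is plausible, although the documents do not say which units sites use.

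What is at stake is mainly consistent handling of subjects: an avoidable permanent stop and a biopsy. Discontinuation due to adverse events is a secondary endpoint (Protocol Section 11.1.2). In the Snapshot classification, subjects who stop for an adverse event before the window count as having no viral load data (SAP Section 4.6.1). Any route from this criterion to those counts is indirect.

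**Working it through.** **Inputs**

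- Fever cut-off for sponsor-defined grade 3 rash: 38 °C or 100 °F (Protocol Section 9.5.2, text and Table 3).
- Fever cut-offs in the grading table: 38.0 °C / 100.4 °F, 38.6 °C / 101.5 °F, 39.3 °C / 102.7 °F and 40.0 °C / 104.0 °F (Protocol Attachment 2, Systemic, Fever).

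**Formulas**

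°F = °C × 9/5 + 32, and °C = (°F − 32) × 5/9.

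**The stated pair**

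- 38.0 × 9/5 + 32 = 100.4 °F, not 100 °F.
- (100 − 32) × 5/9 = 37.78 °C, not 38 °C.
- Gap: 100.4 − 100.0 = 0.4 °F, or 38.00 − 37.78 = 0.22 °C.

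The stated pair cannot be reproduced as a single threshold.

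**Is this just the rounding used elsewhere in the protocol?** The same conversion applied to Attachment 2:

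| °C printed | °F printed | °F computed | Difference (°F) |
|---|---|---|---|
| 38.0 | 100.4 | 100.40 | 0.00 |
| 38.6 | 101.5 | 101.48 | 0.02 |
| 39.3 | 102.7 | 102.74 | 0.04 |
| 40.0 | 104.0 | 104.00 | 0.00 |
| 38 (rash criterion) | 100 | 100.40 | 0.40 |

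The four cut-offs in Attachment 2 agree to within 0.04 °F. The rash criterion is out by ten times that (0.40 / 0.04).

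**What follows for a subject in the band**

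Take a subject with grade 1 or 2 rash, no other added feature, and a temperature of 100.2 °F. In Celsius this is (100.2 − 32) × 5/9 = 37.89 °C.

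- By the Fahrenheit value (100.2 ≥ 100) the rash is grade 3 and study medication must stop.
- By the Celsius value (37.89 < 38) the rash stays grade 1 or 2 and treatment may continue.
- By Attachment 2 (100.2 < 100.4) the temperature is not even grade 1 fever.

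**Reach into the primary endpoint**

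Among those who stop early, Protocol Section 11.5 counts as rebounders only "subjects who discontinued prematurely (irrespective of reason) for which the last available (single) HIV-1 RNA ≥50 copies/mL". A subject stopped under this rule whose last viral load is below 50 copies/mL, with no earlier confirmed rebound, is not a rebounder. The mismatch therefore has no shown effect on the primary comparison.

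**The case against.** The strongest reply is that the rule still gives an answer if read literally. With an or between the two values, meeting either is enough, so 100 °F governs, and the error leans towards stopping drug early in a possible hypersensitivity reaction. That is true, but it makes the 38 °C value redundant, and it lets a temperature below the protocol's own grade 1 fever force a permanent stop. It is also not how a site working in Celsius would read the line.

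A second reply is that the practical effect is very small. The subject needs a rash, no other grade 3 feature and a temperature inside a 0.4 °F band, and temperature is not among the scheduled vital signs (Protocol Section 9.4.4). This stands and limits the weight of the point.

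Third, the rash definition is an explicit sponsor departure from the DAIDS grading, and the DAIDS fever row grades fever as an adverse event, for non-axillary readings only. Being below grade 1 fever there is therefore not in itself an error. This also stands. The error is the unit mismatch; Attachment 2 only shows which pairing the protocol uses elsewhere.

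Fourth, the documents do not state which number was intended. That is fair. Rounding of 100.4 is the likely origin, but it is an inference.

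Finally, Section 9.5.2 leaves management to the investigator within the protocol procedures, and Section 9.5 sends questions to the medical monitor. These give a route for a borderline case, but they do not override a mandatory instruction.

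**Conclusion.** The point holds. The threshold is stated as two different temperatures in both places where it appears, so this is not a text-extraction slip, and the protocol's own grading table gives the correct pairing. The affected band is 100.0 to below 100.4 °F (37.78 to below 38.0 °C). Within it, for a subject with grade 1 or 2 rash and no other added feature, the two values lead to opposite actions, one of which is permanent. The effect is small: the documents give no count of subjects affected, and no effect on the primary comparison is shown. The mismatch itself rests on unit conversion alone. The judgement that 38.0 °C is the intended value rests on Attachment 2 and is likely but not stated. It should be corrected because a mandatory stopping rule needs one threshold.

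**What to change.** In Protocol Section 9.5.2, replace 100 °F with ≥100.4 °F in the running text and in Table 3, so that both agree with 38.0 °C and with Attachment 2. If the sponsor did intend 100 °F, the Celsius value should become 37.8 °C in both places instead; the sponsor should confirm which.

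The cost is a wording correction in two places, with no change to design, sample size or analysis. Because the line governs discontinuation, it may not count as purely logistic or administrative under Protocol Section 17.1, and it would then need a formal amendment with ethics committee approval. The Week 48 analysis had already been done when this SAP was written (SAP Section 1.2), so the correction helps only rash events that occur after it is made.

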# 9.5.3. Acute Systemic Allergic Reaction

Management will be at the discretion of the investigator, taking into account the following protocol-defined procedures (see also Table 4), and should follow generally accepted medical standards.

#### Grade 1

A grade 1 acute systemic allergic reaction is defined as localized urticaria (wheals) with no medical intervention indicated.

Subjects may continue study medication or have their study medication interrupted at the investigator's discretion. The subject should be advised to contact the investigator immediately if there is any worsening of the pruritus, or if any systemic signs or symptoms develop.

Antihistamines or topical corticosteroids or antipruritic agents may be prescribed as long as these are in line with the (dis)allowed medications as indicated in Section 8 or the local Prescribing Information of the ARVs.

#### Grade 2

A grade 2 acute systemic allergic reaction is defined as localized urticaria with medical intervention indicated, or mild angioedema with no intervention indicated.

Subjects may continue study medication or have their study medication interrupted at the investigator's discretion. If there is any worsening of the allergic reaction, the subject should be advised to contact the investigator immediately and to discontinue study medications. Antihistamines or topical corticosteroids or antipruritic agents may be prescribed as supportive care as long as these are in line with the (dis)allowed medications as indicated in Section 8 or the local Prescribing Information of the ARVs.

#### Grade 3

A grade 3 acute systemic allergic reaction is defined as generalized urticaria, or angioedema with intervention indicated or symptoms of mild bronchospasm.

Subjects will permanently discontinue study medication. Subjects will be treated as clinically appropriate. Standard management should be undertaken.

#### Grade 4

A grade 4 acute systemic allergic reaction is defined as acute anaphylaxis, or life-threatening bronchospasm, or laryngeal edema.

Subjects will permanently discontinue study medication. Subjects will be treated as clinically appropriate. Standard management should be undertaken.

DAIDS Toxicity Grade	Definitions	Investigator Action
Grade 1	Localized urticaria (wheals) with no medical intervention indicated	Subject may continue study medication
Grade 2	Localized urticaria with intervention indicated, or mild angioedema with no intervention indicated	Subject may continue study medication
Grade 3	Generalized urticaria, or angioedema with intervention indicated, or symptoms of mild bronchospasm	Permanently discontinue study medication
Grade 4	Acute anaphylaxis, or life-threatening bronchospasm, or laryngeal edema	Permanently discontinue study medication

 Table 4:
 Summary of Allergic Reaction Follow-up

# 9.5.4. Potential Renal Toxicity

Estimated glomerular filtration rate for creatinine clearance (eGFRcr calculated according to the Cockcroft-Gault formula and the CKD-EPI formula), and eGFR for cystatin C clearance (eGFRcyst calculated according to the CKD-EPI formula) will be followed postbaseline during the treatment phase of the study. The eGFRs calculations will be performed and provided to the investigator by the central laboratory.

During the extension phase of the study, eGFRcr according to the Cockcroft-Gault formula for creatinine clearance will be monitored. All subjects with eGFRcr <50 mL/min must have serum creatinine re-measured preferably within 3 calender days of receipt of results. At the time of this repeat serum creatinine assessment, cystatin C will also be measured and the eGFRcyst will be calculated and compared with the baseline measurement.

- eGFRcr according to the Cockcroft-Gault formula:

Male: 
$$(140 - \text{age in years}) \times (\text{weight in kg}) = \text{eGFRcr} (\text{mL/min})$$
  
72 × (serum creatinine in mg/dL)

Female: (140 – age in years) x (weight in kg) 
$$\times$$
 0.85 = eGFRcr (mL/min)  
72 × (serum creatinine in mg/dL)

- eGFRcr and eGFRcyst according to the CKD-EPI formula:

#### eGFRcr

Female:	$Scr \leq 0.7 \text{ mg/dL}$	144 x $(Scr/0.7)^{-0.329}$ x 0.993 age
	Scr > 0.7 mg/dL	144 x $(Scr/0.7)^{-1.209}$ x 0.993 age
Male:	$Scr \leq 0.9 \text{ mg/dL}$	141 x (Scr/0.9) -0.411 x 0.993 age
	Scr > 0.9 mg/dL	141 x (Scr/0.9) -1.209 x 0.993 age
eGFRcyst		
	Scyst $\leq 0.8 \text{ mg/L}$	133 x $(Scyst/0,8)^{-0.499}$ x $0.996^{age}$ [x 0.932 if female]
	$S_{cyst} > 0.8 \text{ mg/L}$	133 x $(S_{cyst}/0,8)^{-1.328}$ x $0.996^{age}$ [x 0.932 if female]

Scr = serum creatinine (mg/dL), Scyst = serum cystatin C (mg/L)

Any subjects who have an eGFRcr (by Cockcroft-Gault) <50 mL/min, and who also experience >20% reduction in eGFRcyst (by CKD-EPI) from baseline, or who have other clinical and/or laboratory evidence of acute renal failure will be discussed with the sponsor's medical monitor and may permanently discontinue study drugs. For subjects with eGFRcr <50 mL/min who are not discontinued based on toxicity management procedures above and considered to have stable renal function per principal investigator and medical monitor, it is not mandatory to repeat eGFR assessments within 3 days.

All subjects with negative or trace proteinuria at baseline who develop >1+ proteinuria on urinalysis must have a urinalysis repeated, with a concurrent urine chemistry, within 2 weeks of receipt of results. Upon confirmation of proteinuria, subjects will be asked to return to the clinic for a scheduled or unscheduled FU visit. It is recommended that the investigator contact the sponsor's medical monitor to discuss if further consultation with a nephrologist is clinically warranted.

Once an individual subject has developed any of these renal changes and the above management guidelines have been applied, it is not necessary to further unscheduled repeat evaluations if it is determined that it is safe for the subject to continue on treatment with standard visits as described in the protocol.

For subjects who are randomized to the control arm, please refer to the local Prescribing Information of Truvada® with regard to dose adjustment or treatment discontinuation in case of renal impairment.

# 9.5.5. Potential Bone Toxicity

As there is uncertainty surrounding the clinical significance and management of decreases in BMD for HIV-1 positive patients, the sponsor recommends that any subject who has a DXA scan that demonstrates a decrease from baseline of >5% in the spine region or >7% in the hip region should be followed per local medical practice at the discretion of the investigator.

# 9.5.6. Potential Posterior Uveitis Cases

In a 9-month toxicology study conducted in dogs, some animals administered the highest dose of TAF (12-18 mg/kg) had minimal mononuclear cell infiltration in the posterior uvea, considered secondary to general debilitation; this finding did not occur in animals given lower doses and it has not occurred in other animal studies. This preclinical finding has also not been observed in humans where the dose is much lower, nor have there been reports of posterior uveitis in human clinical studies. More than 3,000 HIV-positive subjects have been exposed to TAF as part of the Phase 2 and 3 E/C/F/TAF clinical development program by GSI and no AEs consistent with posterior uveitis in humans have been reported. Nonetheless, if subjects develop signs or symptoms of posterior uveitis –which include notable eye pain or redness, reduced visual acuity, or "floaters"- investigators in this study should inform the sponsor's medical monitor and determine, based on their medical judgment the need for prompt referral of the subject for specialized ophthalmologic evaluation including dilated fundoscopy, and if required, optical coherence tomography.

# 9.5.7. Hyperglycemia

Grade 3: 13.89–27.75 mmol/L (>250-500 mg/dL)

#### Grade 4: >27.75 mmol/L (> 500 mg/dL)

Toxicity management decisions should be based on fasted results. If elevated glucose levels are from a nonfasted blood draw, the draw must be repeated after an 8-hour fast.

Subjects who experienced asymptomatic glucose elevations of grade 3 and subjects with preexisting diabetes who experienced asymptomatic glucose elevations of grade 4 may continue study medications unless clinical assessment foresees an immediate health risk to the subject. Appropriate clinical management of hyperglycemia must be started in a timely fashion if applicable. Subjects with persistent grade 3 or 4 glucose elevations despite appropriate antihyperglycemic treatment should permanently discontinue study treatment.

